5.7.3. Analysis Populations

There are a few analysis populations of interest in this study for tabular summaries and/or modeling. Patient populations are described below and presented graphically in Figure 3 to illustrate subsets.

Figure 3 Summary of Populations

New User Cohort: These patients meet the inclusion/exclusion criteria in the protocol regarding being classified as new users of ICS-containing medications or LABD with HES linkage.

New Users without HES Linkage: These patients meet the inclusion criteria 1-5 and Exclusion criteria 1 except for the fact that they are missing the HES linkage (e.g., they

fail inclusion criteria 6, 7). These individuals will be described to compare to the New User Cohort group in the study who have the HES linkage.

New User Cohort Free of Pneumonia at Index Date: These patients are a subset of new users that are at risk of pneumonia at the time of their new use. Patients in the new user cohort who are experiencing an episode of pneumonia that is on-going or has not been resolved for at least 14 days prior to their index date will be excluded from this cohort.

New Users with HES Linkage Excluded from Final Analysis: These patients meet all inclusion/exclusion criteria except are excluded for having an influential propensity score weight or on-going pneumonia or at the time of entry into the New User Cohort.

Final Analysis Population: These patients are a subset of the New User cohort who have PS within an acceptable range, were not experiencing a pneumonia episode at the time of their Cohort Entry Date, and had HES and CPRD data during the period following the Cohort Entry Date.

Pneumonia Population: These patients are a subset of the New User Cohort free of pneumonia at index date and have experience at least one pneumonia event in the year following Cohort Entry, regardless of censoring status in the Cox modeling. The first pneumonia event will be tabulated as either HAP (most severe), severe HAP (less severe), or non-severe CAP (least severe) to count patients in one category. These patients will be compared to those new users free of pneumonia at the Cohort Entry Date who do not develop pneumonia in the year following Cohort Entry.

5.7.4. Multivariable Modeling

Multivariable analysis will be performed using Cox proportional hazard model with adjustment for confounders and exposures in Section 5.6 and Section 5.7.

The following outcomes will be examined:

- Severe pneumonia events (HAP and Severe CAP combined)
- All pneumonia events

Severe pneumonia events will be examined as the primary outcome. As a secondary outcome, all pneumonia events will be analyzed. The number of confounders can be supported in the modeling will be based on the total number of severe pneumonia and all pneumonia events and their distribution by treatment.

To adjust for differences confounding by severity due to differences in prescribing between ICS-containing medications and LABD, propensity scores (PS) will be utilized. The propensity score will be estimated to model the probability that a chance of a patient receiving ICS-containing medications compared with receiving LABD given a patient's observed set of baseline covariates. The logistic models used to calculate the propensity scores, all available variables in Section 5.5 (exposures) and in Section 5.6 (confounders) will be entered into the model. Propensity scores will be produced.

The PS in both groups would be evaluated for overlap, and patients with scores in the tails of the distribution that were not represented in both groups would be eliminated from the analysis. Patients with extreme PS weights (values >10) will be examined and may be removed from the analysis as their contribution would be influential and affect the model. Patients eliminated from the analysis would be described.

Multivariable analysis will be performed using Cox proportional hazard model with adjustment for the propensity score using inverse probability of treatment weighting (IPTW). This approach is more appropriate then propensity score matching when there may be effect measure modification [Stürmer, 2006]. Because of the cohort design, it is possible to adjust for confounders in the PS approach as well as include them as main effects in the model; however, it has been demonstrated that the addition of confounders with propensity scores does not contribute appreciably to the model [Rubin, 2000; Stürmer, 2006]

Parameterization of the explanatory variables in the propensity score generation and subsequent modeling will be based on determining the most appropriate measure (e.g., number of moderate exacerbations may be collapsed into ordinal categories or yes/no if there are few patients with more than 1 in the Baseline Period.) Imputation, removal of outliers, and parameterization of variables for the model will be described in the analysis plan and determined prior to fitting final outcome models.

For the primary analyses (severe CAP and HAP combined), patients will be followed using a Cox proportional hazards model until they experience the first of the following events or censoring: (1) pneumonia event of interest (based on their first pneumonia episode following Cohort Entry), or censoring for (2) death (competing cause), (3) other pneumonia event of interest prior to severe event (competing cause), (4) cohort exit / transfer, practice stopped participating, or end of CPRD follow-up, (5) new user treatment ends, (6) LABD new user is prescribed an ICS, or (7) end of HES follow-up (). Each patient will have a time and "censoring" variable, which is an indicator variable (yes/no) that indicates 1 if they have had the event of interest or 0 if they are censored.

For the analysis of all pneumonia patients will be followed using a Cox proportional hazards model until they experience any pneumonia event (as their first pneumonia episode) or censoring.

To test proportionality of the hazard functions, model diagnostics will be evaluated by including time-dependent covariates in the Cox model. The primary outcomes will be severe pneumonia, (defined as severe CAP and HAP). As a secondary analysis, all pneumonia will be examined.

If one of the explanatory variables is not proportional, we will consider alternatives (time-dependent variable for the non-proportional predictors or stratification on the non-proportional predictors).

If the number of confounders requires reduction to be supported in the Cox model (based on feasibility), a variable selection strategy may be employed as described in the analysis plan.

Interactions between explanatory variables will be determined based on available theory and include ICS/LABD medication use by known risk factors for pneumonia (BMI, age, GOLD stage III/IV, MRC \geq 4, history of pneumonia, current smoking status, deprivation quintiles). Additional interactions may be evaluated with ICS and other patient characteristics.

Additional analysis or adjustments to the analytic or modeling strategy will be performed if the data warrants. A more detailed modeling strategy, including generation of the propensity scores and Cox modeling, will be provided in the analysis plan.

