ICS New Users. Patients will have at least one prescription for ICS-containing medications from January 2002 (the earliest use) until December, 2010 preceded by a year of no use of ICS-containing medications (ICS monotherapy or ICS/LABA fixed dose combination or ICS/SABA) or LABA or LAMA prior to the new user prescription. At Cohort Entry, Patients who are new users of ICS monotherapy or ICS+LABA or ICS+LAMA in separate inhalers could be included as new users. However, patients prescribed new use of triple therapy (ICS, LAMA, LABA) would be excluded from this analysis.

LABD New Users. Patients will have at least one prescription for LABA or LAMA (but not both) from January 2002 (the earliest use) until December, 2010 preceded by a year of no use of ICS-containing medications (ICS monotherapy or ICS/LABA fixed dose combination or ICS/SABA) or LABA or LAMA prior to the new user prescription.

By definition, patients prescribed new use of triple therapy (ICS, LAMA, LABA) would be excluded from this analysis.

Algorithm to Identify New Users. To identify new users, the following algorithm would be employed. First, patients will be evaluated to see if identify their first prescription of LABD in the analysis period (2002 through 2010). Next patients would be evaluated to see if they are new users of ICS-containing medications in a similar manner. Patients

will be included in the analysis only once. As patients could conceivably qualify as new users more than once during the study period or be on more than one medication during the study period, the first prescription defining a patient as eligible for the study (either as new user of LABD or new user of ICS) during the study period only would be evaluated. As patients generally tend to fill multiple prescriptions for COPD in a year and add therapies rather than switch therapies in COPD, subsequent prescriptions would not be evaluated for new use moving forward to the end of available data, as this is expected to yield few patients. In the case of data anomalies where a patient is prescribed ICS/LABA fixed dose combination with either LABA or ICS monotherapy, the patient will be considered as having an ICS/LABA new user prescription.

The date when patients become new users of LABD or ICS-containing medications is considered the **Cohort Entry Date**.

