5.2.2. Inclusion / Exclusion Criteria

Inclusion Criteria

Patients are required to:

- 1. Have CPRD-GOLD data of acceptable research quality according to CPRD standards.
- 2. Be new users of LABD or ICS-containing medications from January 2002-December 2010
- 3. Have a COPD diagnosis at any time in the period prior to and including the Cohort Entry Date (to eliminate any patients with asthma only)
- 4. Have at least one year of data prior to Cohort Entry Date.
- 5. Be at least 45 years of age at Cohort Entry Date.
- 6. Have GPRD-HES linkage. (Note: these individuals need to be retained for basic demographics but are not part of the new user cohort).
- 7. Have HES coverage one year prior to the Cohort Entry Date

Exclusion Criteria

1. Patients with an occurrence of a code for a medical condition incompatible with COPD diagnosis any time in their history. This list contains conditions that are a related to lung or bronchial developmental anomalies, degenerative processes (cystic fibrosis, pulmonary fibrosis), bronchiectasis, pulmonary resection or other significant respiratory disorders other than COPD (but not including cancer) that can interfere with clinical COPD diagnosis or substantially change the natural history of the disease.

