5.5. Exposure

The primary exposure of interest is ICS, evaluated in new user cohort of ICS-containing medications. The comparator exposure group of interest is LABD.

To account for poor adherence to respiratory medications, patients will be classified as exposed to study medication for the duration of prescribed therapy plus 30 days. When the duration of prescribed therapy cannot be determined due to missing information, it will be assumed to be a 30-day supply to correspond to the amount of medications in a single inhaler. In the case of a single inhaler, patients will allow for gaps of up to 90 days between prescriptions.

To identify a study population of long-term users, we will conduct a secondary analyses restricted to patients on treatment for greater than 6 months. The long-term users would allow for examination of cumulative doses. Gaps between each dispensing of up to 90 days will be allowed. A patient dispensed a single inhaler on the Cohort Entry Date would be censored at 90 days if they did not have another prescription. A patient dispensed a single inhaler on day 40 would experience 99 days of coverage (i.e., 39 days of coverage for the first inhaler and 90 days for the second inhaler).

The strength of the new user prescribed ICS medication on the Cohort Entry Date will be categorized into equipotent doses of low, medium, and high-dose ICS based on classification according to Figure 3-1 presented in the Global Initiative for Asthma (GINA) guidelines [GINA, 2011]. The strength of the new user prescription would be entered into the Cox model primary outcome models as low, medium, and high relative to LABD (e.g. dummy variables). The strength of the medication will be tabulated based on the prescription on the Cohort Entry Date.

The use of other medications during the one-year **Baseline Period** will be included in the model as a marker of disease severity.

Prescriptions (Yes/No) during the Baseline Period indicative of disease severity. In addition, the number of prescriptions (except oxygen use) for the following will be collected:

- short-acting bronchodilators (short-acting anticholinergics or short-acting betaagonists, including combination inhalers)
- long-term oral corticosteroid use (>4 Rx in 12 months)
- theophyllines

- oxygen use. when recorded (changes in reimbursement censor this information during part of the analysis period, but we will capture what information is available)

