5.6. Confounders

Key risk factors for pneumonia that may also relate to treatment will be measured in the one-year Baseline Period. For the purposes of general co-morbidity assessment and vaccination for pneumonia, a longer history will be examined. Although patients may have varying periods of history, this is not expected to be differentially recorded by treatment (which could result in information bias). A longer look back period is needed to identify co-morbidities given they may not be recorded in the Baseline Period.

Confounders that are based on "counts" of healthcare encounters and exacerbation will be categorized during analysis (e.g., tabular summaries, propensity score creation, Cox modeling).

Variable	Parameterization
Age at Cohort Entry	Age will be treated either as a continuous variable, or as a categorical one (see Table shells for intervals)
Gender	Male=1 or Female=0
Body Mass Index (BMI) during Ever in Patient History	Weight in kilograms divided by height in meters squared, will be utilised as a categorical variable using the following categories widely referenced as WHO classification: Underweight (Below 18.5), Normal (18.5 - 24.9), Overweight (25.0 - 29.9), and Obese (30.0 and greater).
	For modelling, the following cutoff values will also be examined: BMI<21, BMI 21-24.9, BMI ≥25.
Smoking status during Ever in Patient History	Four categories will be created: ex-smoker, current smoker, non-smoker, and unknown smoking status containing patients with missing entries or other types of tobacco exposure (e.g. passive smoking). Non-smoker will be the referent group in modelling.
Overall Social Deprivation Scores for England	The deprivation quintile is derived the 32,482 areas of social deprivation, with 1 being most deprived and 32,482 being least deprived. quintiles will be identified as follows (with least deprived the referent in modelling). Quintiles are provided by CPRD:

Variable	Parameterization
Townsend Scores	Quintile. Townsend scores will be described by quintile, as provided by CPRD-GOLD.
Charlson Co-morbidity index and individual chapters Ever in Patient History (prior to Cohort Entry Date)	Charlson's comorbidity index chapter indicator measures will be created using a recently published algorithm by Khan and colleagues [Khan, 2010] after removing COPD and AIDS from the disease list. Some patients may have COPD and some may not (incident diagnosis). AIDS will be excluded due to very low prevalence in the general population.

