	In addition, individual indicator variables will be retained for conditions that contribute to the overall Charlson index, including indicators for the following (1=Yes, 0=No): • AIDS (excluded) • Cerebrovascular disease • Chronic pulmonary disease (excluded) • Congestive heart disease • Dementia • Diabetes • Diabetes • Diabetes • Diabetes with complications • Hemiplegia and paraplegia • Mild liver disease • Moderate or severe liver disease • Myocardial infarction • Peptic ulcer disease • Peripheral vascular disease • Renal disease • Rheumatological disease
Additional Co	 Metastatic tumour 1=Vas_0=No for each condition (over in the nationt's history)
Additional Co- morbidities Ever in patient history (prior to Cohort entry Date): Depression, Anxiety, Asthma, GERD	 I = r es, 0=No for each condition (ever in the patient's history) Anxiety diagnosis or anxiety medications (since diagnosis is underrecorded) Depression diagnosis or anti-depressants (since diagnosed underrecorded) Asthma diagnosis GERD diagnosis or GERD treatments
Co-Medications of Interest associated previously with CAP in Baseline Period	 Statins ACE-inhibitors Immunosuppressive treatment including antiretroviral medications

Variable	Parameterization
COPD severity during Baseline Period (1-Year Prior to and 3 Mo	will be defined according to GOLD-defined lung obstruction based classification with Gold Stage II as the referent in modeling.
Date)	• COPD diagnosis and spirometry mismatch: COPD diagnosis but not according to spirometry
	• GOLD 0: $FEV_1/FVC \ge 70\%$ and $FEV1\%$ predicted $< 80\%$
	• GOLD 1: FEV ₁ /FVC<70% and FEV1% predicted \geq 80%
	• GOLD 2: FEV ₁ /FVC<70% and FEV1 % predicted \geq 50 - <80%
	• GOLD 3: FEV ₁ /FVC<70% and FEV1% predicted \geq 30 - <50%
	• GOLD 4: $FEV_1/FVC < 70\%$ and $FEV_1 \%$ predicted $< 30\%$
	• Unknown (if missing spirometry during the one-year baseline period to 3 months following Cohort Entry Date)
Number of GP visits in One-Year Baseline Period	One encounter will be allowed per day to avoid counting several records referring to a single healthcare visit.

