	• 31 = Maternity: where the baby was delivered after the mother's admission
	• 32 = Maternity: where the baby was delivered before the mother's admission
	• 81 = Transfer of any admitted patient from another hospital provider other than in an emergency; this does not include admissions to high security psychiatric hospitals (HSPH)
	• 82 = Other: babies born in health care provider
	• 83 = Other: babies born outside the health care

Variable	Parameterization
	 provider, except when born at home as intended 84 = Admission by the admission panel of an HSPH; patient not entered on the HSPH admissions waiting list (not valid for admissions after 31 March 2002) 89 = From the admissions waiting list of an HSPH (not valid for admissions after 31 March 2002) 98 = Not applicable (e.g. other maternity event) 99 = Not known
Number of non-severe CAP Baseline Period (no hospitalization or death)	Number of non-Severe CAP and Dichotomous variable (1=yes, 0=No)
Number of severe CAP in Baseline Period	Number of Severe CAP and dichotomous variable (1=Yes, 0=No)
Number of HAP in Baseline period	Number of HAP and dichotomous variable (1=Yes, 0=No)
Prior vaccination for influenza in Baseline Period	Influenza vaccination in the year prior to cohort entry (1=Yes, 0=No)
Prior vaccination for pneumonia in past 5- years	Pneumococcal vaccination in the 5-year prior to cohort entry based on recommended frequency of vaccination in the UK (1=Yes, 0=No)
Medical Research Council (MRC) dyspnea scale.	 MRC value if recorded in the year prior to 3 months following Cohort Entry Date will be included in modeling. If unknown, "unknown" would be the assigned value. Grade 1: No Dyspnea except on strenuous Exercise Grade 2: Short of breath when walking up a short hill Grade 3: Dyspnea limits walking pace (slower than others) and stops to catch breath Grade 4: Stops to catch breath after walking 100 meters (328 feet) on level ground Grade 5: Dyspnea prevents leaving house and performing Activities of Daily Living Unknown / Unavailable Collapsing of responses into fewer categories will be considered during the analysis
Entry	2007, 2008, 2009, 2010. During modeling, 2002 will be the reference year.

Additional parameterization of the data, including grouping of the count data into categories, will be considered during the creation of PS or modeling based on the distribution of the data. Details of the analysis and modeling strategy will be described in a statistical analysis plan.

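### The covariate list behind the propensity score has year of entry and several severity proxies, but neither time since COPD diagnosis nor season of entry, so both are balanced only indirectly

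*Protocol*

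**What the plan says.** Section 5.7.4 defines the content of the propensity score by reference: "all available variables in Section 5.5 (exposures) and in Section 5.6 (confounders) will be entered into the model". Section 5.5 contributes baseline respiratory prescriptions. Section 5.6 contributes age, gender, BMI, smoking, deprivation measures, Charlson conditions and other comorbidities, co-medications, GOLD airflow class, GP visits, exacerbations, hospital admissions, prior pneumonia, vaccinations, MRC dyspnea grade and year of entry.

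On disease duration, inclusion criterion 3 in Section 5.2.2 asks patients to "Have a COPD diagnosis at any time in the period prior to and including the Cohort Entry Date", with no limit on how long before. The Charlson row of Section 5.6 recognizes the resulting mix: "Some patients may have COPD and some may not (incident diagnosis". The COPD severity row "will be defined according to GOLD-defined lung obstruction based classification with Gold Stage II as the referent in modeling", and it has a level for missing spirometry.

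On calendar time, the readable part of the year-of-entry row lists years only and adds "During modeling, 2002 will be the reference year". The nearest seasonal variable is "Influenza vaccination in the year prior to cohort entry (1=Yes, 0=No", a yes/no over twelve months. Cox time runs in days from entry (Section 5.7.2), and Section 5.5 says that a patient with a single inhaler "would be censored at 90 days if they did not have another prescription".

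**The concern.** The protocol expects prescribing to follow disease stage. Sections 5.2.1 and 5.7.1 describe a LABD as initial maintenance treatment, with ICS added as severity warrants, and Section 6 names confounding by severity as a known limitation. Time since diagnosis is one marker of stage. It can be derived for every patient, because eligibility depends on a dated COPD code. It also remains available when spirometry is missing, or when MRC grade is missing or left out (Section 5.7.5 notes that MRC is collected from 2009 onwards and may not be included). Yet no covariate carries it, not even as an incident/prevalent flag.

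Season raises a smaller question. Because the Cox clock starts at entry, it does not align patients by calendar date. For someone censored at 90 days, the month of entry decides whether any winter is observed. If pneumonia is seasonal and one arm starts treatment in winter more often, early follow-up would differ between arms for a reason unrelated to treatment.

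At stake is a residual multiplier on the hazard ratio for severe pneumonia, the primary outcome.

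**Working it through.** **Step 1: are the variables on the lists?** A line-by-line reading of Sections 5.5 and 5.6 and of table shells 7, 8 and 11 finds no time since or date of COPD diagnosis, no incident/prevalent flag, and no month, quarter or season of entry. The start of the year-of-entry row is cut off in the text at hand.

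**Step 2: can they be derived?** Yes. Criterion 3 requires a COPD diagnosis on or before entry, and Section 5.2.1 fixes an exact entry date for each patient ("The date when patients become new users of LABD or ICS-containing medications is considered the" Cohort Entry Date).

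**Step 3: how long is follow-up?** Section 5.7.8 gives 283 first pneumonia events at 15.8 per 1,000 person-years and 106 severe events at 5.3 per 1,000. Table 1 gives 18,742 new users.
- 283 / 0.0158 = 17,911 person-years; 17,911 / 18,742 = 0.96 years per patient.
- 106 / 0.0053 = 20,000 person-years; 20,000 / 18,742 = 1.07 years per patient.

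Mean follow-up is therefore about one year.

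**Step 4: size for disease duration.** Neither input is in the protocol, so both are assumptions: a hazard ratio h of 1.1 to 1.3 per 5 years of disease, and a gap g of 1 to 2 years between arms that remains after the listed covariates have been balanced. The multiplier is h^(g/5).

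| | g = 1 year | g = 2 years |
|---|---|---|
| h = 1.1 | 1.019 | 1.039 |
| h = 1.3 | 1.054 | 1.111 |

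**Step 5: size for season.** Assumptions: a cosine-shaped hazard peaking in mid-January with a winter-to-summer ratio r of 2 to 3, giving amplitude A = (r − 1)/(r + 1) = 0.33 to 0.50. One arm starts evenly through the year; the other has start density 1 + B·cos with B = 0.2 to 0.3. For follow-up of L days, with starts peaking d days before the hazard peak, the ratio of mean hazards is

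1 + (A·B/2) · [sin(πL/365) / (πL/365)] · cos(2π(L/2 − d)/365).

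| Peak of starts | Oct–Mar share of starts | 90 days | 180 days | 365 days |
|---|---|---|---|---|
| About 1 December (d = 45) | 55.5–58.3% | 1.030–1.068 | 1.015–1.035 | 1.000 |
| Mid-January (d = 0) | 56.0–59.0% | 1.022–1.049 | 1.001 | 1.000 |

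The 1 December row is the worst phase for 90-day follow-up. Across the two rows the range is about 1.02 to 1.07 at 90 days and 1.00 to 1.035 at 180 days.

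**Step 6: scale against random error.** With 106 severe events and an ICS share of 12,065 / 18,742 = 0.644, SE(log HR) ≈ 1/√(106 × 0.644 × 0.356) = 0.203. The 95% limits then lie a factor exp(1.96 × 0.203) = 1.49 either side, before any loss from weighting. The largest duration multiplier, 1.11, is ln(1.11)/0.203 ≈ 0.5 of a standard error; the smallest, 1.019, is about 0.1.

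**The case against.** The strongest reply is that this is an optional covariate choice. Section 5.7.4 says that all listed variables go in, not that only those may. It leaves the detailed generation of the score to the analysis plan, and Section 5.7.9 foresees changes in covariates. That stands in part: the plan could add both variables. But Section 5.6 sets out a long, specific list, and what it and Section 5.7.4 expressly defer is mainly the parameterization, grouping and reduction of listed variables. Nothing commits to adding these two.

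A reader might infer that the score cannot balance duration or season at all. The documents do not support that. Age, GOLD class, MRC grade, exacerbations, GP visits, admissions, long-term oral steroids, oxygen, nebulized therapy and prior pneumonia all carry information on disease stage, and most remain available when spirometry is unknown. Recent exacerbations may also pick up some winter starts.

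A reader might also infer that the hazard ratio is biased. The protocol gives neither disease duration nor month of entry by arm, so an imbalance is plausible but not shown. Its direction is uncertain too, because both arms must have a year free of either drug class before entry.

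Finally, it is fair that the sizes in Steps 4 and 5 are small beside the confidence limits in Step 6 and beside the margins of 2.0 and 1.5 in Section 5.7.8. The objection that more covariates strain 106 events has little force for the score itself, which is a logistic model of treatment fitted on up to 18,742 patients.

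**Conclusion.** The point holds as a modest gap. Two variables that can be derived from data in hand are not on the list that feeds the propensity score, so they are balanced only through proxies. Disease duration matters more: a multiplier of 1.02 to 1.11, resting wholly on an assumed hazard ratio of 1.1 to 1.3 per 5 years and an assumed residual gap of 1 to 2 years. Season is secondary: about 1.02 to 1.07 for patients followed 90 days and 1.00 to 1.035 at 180 days, for an assumed 55 to 59% October–March share of starts in one arm against an even spread in the other, and nil over a full year. With mean follow-up of about one year, season matters chiefly for patients censored early, who each contribute little person-time.

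The seasonal effect should not be taken as persisting at close to its 90-day size. A 180-day multiplier near 1.05 would need the peak of starts moved to about mid-October, where the winter excess of starts is smaller than assumed here. Nothing in the protocol suggests that either omission would by itself change a conclusion about the 1.5 or 2.0 margins.

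**What to change.** Add two rows to Section 5.6 and enter both in the propensity score:

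1. Time from the first recorded COPD code to the Cohort Entry Date, in categories, with an incident level (same day or within 30 days).
2. Calendar quarter of entry.

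Report weighted standardized differences between arms for both, so that any imbalance can be seen. Stratifying the Cox model by quarter is optional and not needed.

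The cost is two derived variables and a few score parameters. There is one small drawback. The first recorded code depends partly on how long a patient has been registered: only one year of prior data is required, and Section 5.6 acknowledges that history varies in length. Categories or an incident/prevalent flag are therefore preferable to a purely continuous term.
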